10.6 Crossover visit (visit 5a)

Only subjects initially randomized to the control group (HA injection) who remain in **significant** pain at Visit 5 are eligible to receive crossover. Significant pain is defined as pain substantial enough to warrant receipt of a minimally invasive procedure (i.e., CRFA) per the investigators and subject assessment. Subjects do not need to formally requalify for the study to receive crossover per the inclusion/exclusion criteria; however, *confirmation and documentation is needed that subjects remain a medically appropriate candidate* for the CRFA procedure in order to be eligible.

Prior to receiving the Crossover procedure, the subject should be reminded of the risks of the CRFA procedure as described in section 4.6 and should sign the Crossover section of the informed consent document as noted in Section 8.2.

If the subject is still receiving relief from the HA injection at the time of this visit and/or is not medically appropriate for the CRFA procedure or elects not to Crossover, the subject should not receive crossover treatment and should continue to complete Visit 6.

It is anticipated that the Crossover procedure will occur on a different day than the 6 Month visit (Visit 5); however, it is allowable to perform the procedure on the same day if the Visit 5 items are completed first. Otherwise, the crossover treatment should occur within 30 days of Visit 5. If Visit 5A occurs on the same day as Visit 5, overlapping assessments noted below that were completed as part of Visit 5 do not need to be re-done (i.e., NRS, WOMAC, Healthcare Utilization, etc.).

If a subject choses crossover, the timing of their follow up visits (5B, 5C and 6) will now be based off their Visit 5A treatment date. Visit 5B/1 Month Visit should occur at post-operative day 30 ± 7 days. Visit 5C/3 Month Visit should occur at post-operative day 90 ± 14 days and the 6 Month Visit/Visit 6 should occur at post-operative day 180 ± 14 days.

At the Crossover Visit, the following assessments must be performed.

- (1) Verify Crossover consent was obtained
- (2) Verify and document that the subject remains medically appropriate for the procedure.
- (3) Obtain a Numeric Rating Scale for pain (subject completed questionnaire).
- (4) Obtain WOMAC Score (subject completed questionnaire).
- (5) Obtain an EQ-5D-5L Assessment (subject completed questionnaire).
- (6) Obtain a Global Perceived Effect Score (subject completed questionnaire).
- (7) Obtain Healthcare Utilization Form
- (8) If applicable, follow site standard procedures for confirming pregnancy status prior to treatment.
- (9) Perform CRFA procedure per section 6.6.4.
- (10) Perform adverse event assessment.
- (11) Assess concomitant medications.
- (12) Provide subject with perioperative care and at home care instructions.
- (13) Schedule next clinic visits (1, 3, and 6 months as noted above).

11 ADVERSE EVENT REPORTING

11.1 ADVERSE EVENTS (AE) ASSESSMENT

Subjects should be instructed to contact the Investigator (or designee) immediately if an AE occurs. At each visit, the investigator (or authorized designee) should further query the subject to determine if any

new adverse events have occurred. Adverse Events will be assessed from the time the subject signs consent until study exit. All adverse events must be reported according to the following procedure.

Sites will be instructed to follow their normal /routine processes for adverse event reporting of post market products to the FDA per 803.20 – Individual Adverse Event Reports, however; related events that result in death, serious injury or malfunction that could cause death or serious injury will be specifically monitored for. As an additional measure of control, the sponsor will periodically review reported events as described in section 11.6 looking for items that meet the reporting criteria.

11.1.1 Definitions and Classification

Adverse Event (AE):

Any untoward medical occurrence that occurs in a subject or clinical investigation subject using a study device including any unfavorable and unintended sign (including abnormal laboratory finding), symptom, or disease temporally associated with the use of the study device, whether or not considered related to the device.

Treatment Emergent Adverse Event (TEAE):

An AE that begins or worsens in severity after the subject has used at least one study device

Non-Treatment Emergent Adverse Event:

An AE that begins or worsens in severity between the time that the consent form is signed and the first use of the study device

Serious Adverse Event (SAE):

A Serious Adverse Event is defined as any untoward medical occurrence that falls into one of the following categories:

- A. Results in death
- B. Is life threatening, meaning that the subject is at risk of death at the time of the event; this does not mean that the event hypothetically might have caused death if it were more severe.
- C. Requires inpatient hospitalization or prolongation of existing hospitalization
- D. Results in persistent or significant disability or incapacity
- E. Is a congenital anomaly or birth defect in a subject's fetus or baby
- F. Is an important medical event that may not be immediately life-threatening or result in death or hospitalization, but that may jeopardize the subject or require intervention to prevent one of the above outcomes. Examples of such events are intensive treatment in an emergency room or at home for allergic bronchospasm, blood dyscrasias, or convulsions that do not result in hospitalization.

Version #: 4.0

Version Date: 28Mar19

Unanticipated Adverse Device Effect (UADE):

Any serious adverse effect on health or safety or any life-threatening problem or death cause by, or associated with, a device, if that effect, problem or death was not previously identified in nature, severity, or degree of incidence in the investigational plan or application, or any other unanticipated serious problem associated with the device that relates to the rights, safety, or welfare of subjects.

11.2 SEVERITY OF ADVERSE EVENTS

The Investigator (or authorized delegate) will assess the severity of each AE based on the following definitions:

Severity	Definition
Mild	An AE in which the subject is aware of signs or symptoms, but which does not interfere with
	the subject's usual activities of daily living, or is transient and resolves without treatment or
	sequelae
Moderate	A sign or symptom which interferes with the subject's usual activities of daily living or
	requires treatment
Severe	An AE that results in incapacity with inability to do work or do usual activities of daily living.
	Severe AEs require treatment or medical intervention to resolve

11.3 RELATIONSHIP OF ADVERSE EVENTS

For each AE, the Investigator (or qualified delegate) will assess the causality/relationship to the investigational device according to the following criteria:

Relatedness	Definition
Unrelated	A clearly evident relationship to other etiologies, such as concomitant medications or conditions or subject's known clinical state
Unlikely	Based upon available information regarding subject history or disease process, relationship of adverse event to test article(s) is unlikely
Possible	The association of the AE with the test article is unknown; other etiologies are also possible

Probable	A reasonable temporal sequence of the AE with test article administration exists
	and based upon the medical professional's clinical experience, the association of
	the AE with the test article seems likely
Definite	A causal relationship exists between the test article and the AE, and other
	conditions (e.g., concomitant illness, progression or expression of the disease state,

For AE's, the most likely cause (e.g., disease under treatment, concomitant disease, concomitant medication, other) will be indicated on the eCRF with details of the concomitant disease or medication or other cause.

11.4 REPORTING ADVERSE EVENTS

- A. All AEs must be recorded in the subject's medical record and the appropriate eCRF. The description of the AE will identify the date of onset, date of remission, severity, causal relationship to the study product, action taken along with the results of any diagnostic procedures or laboratory tests, all treatments that were required and the outcome of the event.
- B. The Investigator will follow all study device related AEs until there is a return to baseline or until a clinically satisfactory resolution is achieved.

11.5 REPORTING SERIOUS ADVERSE EVENTS

The Investigator must report any SAE to the Sponsor within 24 hours of becoming aware of the event. All deaths, whether or not considered study-related, must be reported immediately to the Sponsor with a copy of the autopsy report and death certificate provided when and if available.

SERIOUS ADVERSE EVENT REPORTING INSTRUCTIONS

[name], MBBCh FCSSA PhD

Medical Monitor

[contact]

Email: [contact]

Fax/Scan the Serious Adverse Event form and supporting documentation to [contact] within 24 hours of becoming aware of a Serious Adverse Event.

The Investigator and the Sponsor will review each SAE report to evaluate the seriousness and the causal relationship of the event to study device. In addition, the Sponsor will determine if that effect, problem, or death was not previously identified in nature, severity, or degree of incidence in the investigational plan. Based on the Investigator and Sponsor's assessment of the event, a decision will be made concerning the need for further action.

All SAEs will be captured from signing of informed consent throughout the study. The Investigator must notify the IRB in writing of all SAEs in accordance with IRB requirements.

11.6 CLINICAL SAFETY MONITORING

Avanos Medical's Medical Director will conduct periodic safety monitoring and oversight throughout the course of the study by reviewing all Serious Adverse Event reports, conducting Adverse Event listing reviews, and monitoring post-market surveillance reports.

Upon receipt of any Serious Adverse Event (SAE) report at Avanos Medical, the medical monitor will review the SAE report for completeness and when necessary, will request clarification and/or additional information from the investigator. The designated medical monitor is responsible for reviewing the investigator's assessment and classification of each event. If the designated medical monitor disagrees with the investigator's classification of the event, the rationale will be provided to the investigator. If the investigator agrees with the designated medical monitor, the subject's Adverse Event Report Form will be updated accordingly. If the investigator does not agree with the designated medical monitor classification, both determinations will be documented within the study report. However, the Avanos Medical determination will be used for analysis purposes.

Given the 'Exempt' status of this study, Avanos Medical has determined that a Data Monitoring Committee (or DSMB) is not required based on the FDA guidance document, "Establishment and Operation of Clinical Trial Data Monitoring Committees".

12 STATISTICAL METHODS AND DATA ANALYSIS

Prior to initiation of the analysis, a stand-alone Statistical Analysis Plan (SAP) will be prepared, which will provide detailed methods for the analyses outlined below. Any deviations from the planned analyses will be described and justified in the final integrated study report.

The primary analysis is planned when the last enrolled subject completes the 6-month follow-up visit. The subjects will continue to be followed through 12 months, and a final analysis is planned at the conclusion of the study after the last subject completes the 12-month follow-up visit.

An additional analysis will be conducted once the last subject completes the extension study to analyze data collected at 18 and 24 months.

12.1 DETERMINATION OF SAMPLE SIZE

A non-inferiority approach on response rate was used to estimate the sample size for this study, with "response" defined as \geq 50% reduction in pain on the NRS scale from baseline. The upper bound of a 2-sided 95% CI will be calculated for the rate difference between treatments (Standard minus Test). If the upper bound is less than (δ), then "non-inferiority" is achieved for the test treatment relative to standard treatment, as described in the table below:

Success Rate of CRFA (based on 50% Pain Score Reduction in VAS)	Success Rate of Standard (Based on 30% Pain Score Reduction in VAS)	Non-Inferiority Margin (δ)	Sample Size 5% Level of Significance (2-sided) 90% Statistical Power
62%*	40%**	5%	134

^{* - 14} Davis, et al, RAPM 2017, In Press /FDA clearance K163461

Assuming an attrition rate of 20%, 168 subjects enrolled into the study will yield 134 completers.

12.1.1 Disposition of Subjects

The number and percentage of subjects entering the study will be presented. Reasons for any screen failures and/or early terminations will be summarized. A flow chart will present the aggregate disposition of subjects from Visit 1 (Screening Visit) through the final 24-month visit, including all subjects who cross over from the viscosupplementation injection group to the CRFA denervation group.

12.1.2 Protocol Deviations

Deviations from the protocol, including violations of inclusion/exclusion criteria, will be assessed as "minor" or "major" by the sponsor prior to database lock and analysis. Major deviations from the protocol will lead to the exclusion of a subject from the Per-Protocol Set.

Certain clinical situations may require waivers for the safety of the subjects enrolled, integrity of the data or scheduling conflicts. Any waiver request will be reviewed on an independent basis and must be documented in writing prior to the event occurrence. Clinical decisions will be made by the medical monitor.

^{** - &}lt;sup>5 Chevalier, X et al. "Single, intra-articular treatment with 6 ml Hylan G-F 20 in patients with symptomatic primary osteoarthritis of the knee: a randomized, multi-center, double-blind, placebo controlled trial" *Ann Rheum Dis* 2010 69: 113-119.

12.2 DATASET DEFINITIONS

12.2.1 Safety Set

All randomized subjects who receive CRFA or HA injection treatment will be included in the safety analyses.

12.2.2 Full-Analysis Set

All randomized subjects will be analyzed following the principle of intention-to-treat (ITT) provided they received CRFA or HA injection treatment and had at least one effectiveness observation.

12.2.3 Per-Protocol Set

All randomized subjects who are compliant with the study protocol (i.e., who do not experience any major protocol deviations) and who receive CRFA or HA injection treatment and have at least one effectiveness observation will be included in the Per-protocol Set.

The primary effectiveness endpoint analysis will be based on the Full Analysis Set, although a secondary analysis will also be performed based upon the Per-Protocol Set (if there are differences), to assess the sensitivity of the analysis to the choice of analysis population. The analyses of all other endpoints will be based upon the Full Analysis Set only unless otherwise stated in the SAP. All safety analyses will be based upon the Safety Set.

Crossover subjects that continue to meet all Inclusion/Exclusion criteria will be included in the Perprotocol Set, and may be combined with CRFA randomized subjects for purposes of overall assessment of the CRFA procedure.

12.3 EFFECTIVENESS PARAMETER

12.3.1 Primary Effectiveness Parameter

The primary effectiveness parameter is defined as the proportion of subjects whose knee pain is reduced from baseline by \geq 50% based on the Numeric Rating Scale (NRS) at the 6-month visit.

12.3.2 Secondary Effectiveness Parameters

Secondary Effectiveness Endpoint 1: The proportion of subjects whose knee pain is reduced from baseline by $\geq 50\%$ based on the Numeric Rating Scale (NRS) at the 12-month visit.

Secondary Effectiveness Endpoint 2: The change in the WOMAC Score from baseline to the 6 month visit and 12-month visit.

12.3.3 Tertiary Effectiveness Parameter

Tertiary effectiveness endpoint 1: The change in measured EQ-5D-5L scale from baseline at the 6-month visit and 12-month visit.

Tertiary effectiveness endpoint 2: The measured Global Perceived Effect scale at the 6-month visit and 12-month visit.

12.3.4 Exploratory Analysis

Other variables of interest, which include, but are not limited to, WOMAC subscale analysis (pain, stiffness, physical function), change in pain medication usage from baseline as measured by subject self-reported average daily dosage, healthcare utilization, and change in weight from baseline, will be summarized at various visit intervals as discussed below in section 12.5.

In addition, the endpoints listed above will also be summarized at 18 and 24 months post treatment.

12.4 GENERAL CONSIDERATIONS

All statistical tests will be two-sided and will be performed at the 5% level of significance, unless otherwise stated in the statistical analysis plan (SAP). Continuous data will be summarized by randomized device assignment and other subset (center, age, etc.) groupings using descriptive statistics (number, mean, median, standard deviation [SD], minimum, and maximum). Categorical data will be summarized by randomized device assignment and other subset groupings using frequency tables (frequencies, percentages, confidence intervals). The natural log transformation will be applied to variables which are highly skewed. If the model assumptions for the ANOVA are not met, transformation of the data or non-parametric analysis may be implemented.

12.5 DEMOGRAPHICS, BASELINE CHARACTERISTICS, AND CONCOMITANT MEDICATIONS

Demographic data, medical history, and concomitant medications will be summarized by means of descriptive statistics.

ΔVΔNOS

Confidential

12.6 **EFFECTIVENESS ANALYSES**

12.6.1 Primary Effectiveness Analysis

The primary efficacy parameter is the response rate which is defined as the proportion of subjects whose knee pain is reduced from baseline by ≥ 50% based on the NRS scale at 6 months after treatment.

Each subject's response to the treatment will be treated as an independent binomial event:

 H_0 : πc - πτ ≥ 0.05

Ha: $\pi_C - \pi_T < 0.05$

Where:

 Π_T : proportion of subjects with $\geq 50\%$ decrease from baseline in NRS pain score from baseline at the 6

months post randomization in the CRFA group

Πc: proportion of subjects with ≥ than 50% decrease from baseline in NRS score from Screening at the 6

months post randomization in the HA injection group

The non-inferiority margin is set at 5% for the primary efficacy parameter expressed as proportion. The difference of proportions between treatment groups will be calculated and a two sided 95% confidence interval will be constructed using Wald asymptotic confidence limits approach or exact binomial limits approach. If the upper bound is less than 0.05, then 'Non-inferiority' is established for the CRFA group relative to the HA injection group. If, in addition, the upper bound of the confidence interval is below zero,

the CRFA group can be determined to be 'Superior' to the HA injection group.

Treatment by study center interaction may be examined graphically across study center to determine the association between treatment and response rate is in the same direction or using logistic regression with response rate at 6 months as the response variable, and the study center, treatment group, study center

by treatment group interaction as predictor variables in the model.

12.6.2.2 WOMAC

The change in the WOMAC Score from baseline to the 6 month and 12 month visits will be calculated and compared between the two treatment groups:

 H_0 : $\mu_1 = \mu_2$

 H_a : $\mu_1 \neq \mu_2$

Where:

μ₁: mean of WOMAC Score change between the Baseline and the Follow-Up at 6 months and 12 months for the CRFA group

μ₂: mean of WOMAC Score change between the Baseline and the Follow-Up at 6 months and 12 months for the HA injection group

Analysis of variance (ANOVA) with treatment as fixed effect and study center as block effect on changes in the WOMAC between the Baseline and the Follow-Up at 6 months and 12 months separately will be performed for the comparison of the CRFA with the HA injection groups.

Treatment by study center interaction may be examined using analysis of variance (ANOVA) with treatment, study center and treatment by study center interaction effects on changes in the WOMAC between the baseline and the Follow-Up at 6 months and 12 months in the model.

12.7 SAFETY ANALYSES

12.7.1 Safety Parameter

All adverse events that occur during the study will be recorded per the protocol definitions. An overall adverse event rate will be summarized for both treatment groups.

12.7.2 Method of Analysis

Adverse events occurring during the study will be tabulated by body system, severity, and Investigator reported relationship to the study device. Any deaths or serious device associated AEs will be summarized. From enrollment to follow up visit at 6 months, adverse events will be stratified by subjects randomization assignment. After follow up visit at 6 months to follow up visit at 12 months (end of study), adverse events will be stratified among subject status between CRFA, HA and Crossover.

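### Section 12.7.2 summarizes non-fatal serious adverse events only when they are device associated, so the supplied text specifies no all-cause SAE count by arm

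*Combined protocol and SAP*

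**What the plan says.** Section 12.7.1 plans an overall AE rate for both groups. Under section 12.7.2, adverse events are "tabulated by body system, severity, and Investigator reported relationship to the study device". Serious events appear in one sentence: "Any deaths or serious device associated AEs will be summarized". The rest of 12.7.2 splits adverse events by randomized arm up to the 6-month visit, then by CRFA, HA and Crossover status up to 12 months. The analysis population is set in 12.2.1: "All randomized subjects who receive CRFA or HA injection treatment will be included in the safety analyses".

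Collection is wider than this summary. Section 11.1.1 defines an SAE by its outcome, with no condition on cause, and 11.5 states: "All SAEs will be captured from signing of informed consent throughout the study".

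Attribution is covered in two places. Section 11.3 gives five grades, from Unrelated to Definite. Section 11.6 has the sponsor's medical monitor review the investigator's classification of each SAE. If they still disagree, both views go into the study report, and then: "However, the Avanos Medical determination will be used for analysis purposes".

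**The concern.** Section 5 includes an objective to confirm the safety of CRFA compared with HA. The primary safety endpoint in 6.2.1 counts subjects with any adverse event, so a mild bruise and a hospital admission weigh the same. The serious-event summary is where a reader would look for the difference. As specified, a non-fatal event reaches it only if someone attributes it to a device.

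No blinding is described. The bias measures in 6.3 rely on subject-reported effectiveness endpoints, screening log review and independent monitoring, data management and statistics. None of these protects causality grading from knowledge of the arm. A count of SAEs regardless of cause does not depend on that grading.

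**Working it through.** The plan states no figure on this point, so the check sets the planned safety outputs side by side.

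| Planned output | Events included | Identifies serious events? |
|---|---|---|
| Primary safety endpoint (6.2.1) and overall rate (12.7.1) | Any AE | No |
| Tables by body system, severity and relationship (12.7.2) | All AEs | No |
| Splits by arm to 6 months and by status to 12 months (12.7.2) | All AEs | No |
| Serious-event sentence (12.7.2) | Deaths; device-associated SAEs | Yes, but non-fatal events only if attributed |

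**Can severity stand in for seriousness?** No. Section 11.2 defines Severe as "An AE that results in incapacity with inability to do work or do usual activities of daily living". Section 11.1.1 defines seriousness by death, threat to life, hospitalization, disability, birth defect or an important medical event. An inpatient admission is serious whatever its severity grade. A short spell of incapacity treated as an outpatient may be severe without being serious. The two overlap but neither gives the other.

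**Follow one event through the plan.** Take a non-fatal hospitalization in the CRFA arm at month 3.
- Graded Unrelated, it counts in the overall AE rate, in a body-system row, in a severity row and in the CRFA column. It does not enter the serious-event summary.
- Graded Definite, with nothing else changed, it does enter that summary.

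The causality grade alone decides whether it is shown as serious.

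**Is the filter well defined?** Not fully, in two respects.
- No section says which grades in 11.3 count as device associated. The grade Possible, described as "The association of the AE with the test article is unknown; other etiologies are also possible", could fall on either side.
- The 12.7.2 tables use the investigator's grade, while 11.6 uses the sponsor's determination for disputed SAEs. The text does not say which applies to the serious-event sentence.

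**Size.** Approximately 168 subjects at 1:1 gives 168 / 2 = 84 per arm, taking all as treated. The documents give no all-cause SAE rate for this study, so the risk below is an assumption:
- 2%: 84 × 0.02 = 1.7 subjects
- 5%: 84 × 0.05 = 4.2 subjects
- 10%: 84 × 0.10 = 8.4 subjects

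These are all subjects with a non-fatal SAE, so they are an upper limit on the number not shown as serious. The actual number depends on the grades given and cannot be derived from the documents.

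**The case against.** The strongest reply is that 12.7 is an outline. Section 12 promises a stand-alone SAP with detailed methods, and the serious-event sentence does not exclude other summaries. This stands in part: the SAP could add an all-cause table. But the outline does more than stay silent, because it states a rule with a relationship condition in it, and an SAP that only elaborated that rule would keep the condition.

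A second reply is that nothing is lost. This is correct as far as it goes. Every SAE is an AE, all are captured, deaths are summarized whatever the cause, and the data could be retabulated at any time. What is missing is the identification of the remaining events as serious, by arm.

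Four stronger readings are tempting, and the documents do not support them.
- *The plan drops or conceals unrelated SAEs.* They remain in the overall rate and the by-arm tables.
- *The sponsor replaces the investigator's judgment in general.* Section 11.6 applies this only where disagreement over an SAE persists, and both determinations are documented. A specific rule for disputed SAEs can coexist with an investigator-graded table of all AEs. One clarifying sentence would settle it.
- *Safety after 12 months is left out.* The grouping in 12.7.2 does stop there, but 6.2.1 runs to final follow-up, 6.2.4 summarizes endpoints at 18 and 24 months, and section 12 plans an analysis of the extension data.
- *The Synvisc-One instructions in Appendix 2 show how many SAEs a relationship filter removes.* Their tables by relatedness concern adverse events in the injected knee, and the same text reports no serious ones there in either arm. They cannot size this point.

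**Conclusion.** The point holds in a limited form. The supplied text specifies a serious-event summary for deaths and device-associated SAEs and no all-cause SAE count by arm. The comparison of non-fatal serious events would then depend on attribution made without described blinding, with an unstated grade cut-off and with the sponsor's view used in unresolved disputes.

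The number of SAEs affected is unknown; the 2 to 8 subjects per arm rests on the assumed 2% to 10% risk and is an upper limit within that range. The conclusion also assumes that the stand-alone SAP, which is not among the supplied documents, does not already add the table. Sample size and the effectiveness conclusions are unaffected. Severity is minor: a cheap improvement to reporting.

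**What to change.** Replace the serious-event sentence in 12.7.2 with:

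> All deaths and all serious adverse events, regardless of relationship, will be summarized as number and percent of Safety Set subjects with at least one treatment-emergent SAE, by randomized arm to the 6-month visit and descriptively by CRFA, HA and Crossover status thereafter (CRFA only in the extension). SAEs before first treatment will be listed separately. Device-associated SAEs will be shown as a subset, by investigator grade and, where different, sponsor grade.

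State alongside it which of the five grades in 11.3 count as device associated.

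The later periods are descriptive because crossover is chosen by HA subjects still in significant pain (10.6) and the extension has no HA arm (10.4). Pre-treatment SAEs are kept apart because capture starts at consent (11.5), and an event before treatment should not count against an arm.

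The cost is about one extra table from data already collected under 11.5 and 11.6. The downside for the sponsor is that the reported serious-event count may be higher than the filtered one.

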6 INVESTIGATIONAL PLAN

6.1 STUDY DESIGN

[figure not shown]
This is a prospective, randomized, multicenter comparison study examining the outcomes of subjects with OA and knee pain undergoing a procedure to create a radiofrequency lesion of the genicular nerves with the CRFA system compared to subjects receiving HA. A total of approximately 168 subjects will be enrolled into this study, with subjects undergoing either CRFA or HA injection in a 1:1 randomization scheme. Follow up will be conducted for a total of 12-months post randomized procedure with the

Version #: 4.0

Version Date: 28Mar19

primary endpoint being completed at month 6. Subjects randomized to the comparison (HA) group will have the option to cross over to the neurotomy group after completing the 6-month endpoint assessment. They would then be followed for an additional 6 months. Pain, overall outcome, quality of life, pain medication use, and adverse events will be compared between the two treatment groups in order to determine success. Unless they have received an additional procedure on their index knee, subjects who were randomized to and received CRFA as their initial treatment will have the option to add 2 additional visits at 6-month intervals, representing 18 and 24 months post initial treatment.

CRFA = Genicular Neurotomy using Cooled Radiofrequency Ablation HA = Hyaluronic Acid Injection (Synvisc-One 6 mL injection)

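### Adverse events are grouped by randomized arm from enrollment and regrouped at Visit 5, so an event's group can differ from the treatment last received at its onset

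*Combined protocol and SAP*

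**What the plan says.** Section 12.7.2 splits safety reporting into two periods. In the first, "From enrollment to follow up visit at 6 months, adverse events will be stratified by subjects randomization assignment". From that visit to 12 months, "adverse events will be stratified among subject status between CRFA, HA and Crossover". It does not say when a subject's status becomes Crossover. Section 12.7.1 adds an overall adverse event rate for the two treatment groups. Section 6.2.1 makes the proportion of subjects with adverse events, through final follow-up, the primary safety endpoint. Section 12.2.1 says "All randomized subjects who receive CRFA or HA injection treatment will be included in the safety analyses"; this settles who is included, not the group in which they are counted.

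Under Section 6.1, HA subjects "have the option to cross over to the neurotomy group after completing the 6-month endpoint assessment". Section 10.6 expects the crossover procedure on a different day from Visit 5, but "it is allowable to perform the procedure on the same day if the Visit 5 items are completed first". For all other crossovers the same section sets a limit: "Otherwise, the crossover treatment should occur within 30 days of Visit 5". Visits after crossover are then timed from Visit 5A.

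Section 11.1 collects adverse events from consent to study exit. Section 11.1.1 defines a treatment-emergent event as "An AE that begins or worsens in severity after the subject has used at least one study device" and keeps a separate class for events between consent and first use of a study device. Section 12.7 uses neither term. Section 11.4 records the date of onset and does not ask for the time.

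**The concern.** A safety table should tell the reader what happened after each treatment. Here both boundaries are administrative. The first period opens at enrollment rather than at treatment, and the grouping changes at the 6-month visit rather than at the procedure that changes the treatment.

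Four mismatches are possible:

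- Events before any study treatment enter an arm's table.
- In the first period, a subject given the wrong treatment is counted under the assigned arm.
- An event after Visit 5 but before Visit 5A, when only HA has been given, can appear under Crossover.
- With same-day crossover, a CRFA procedure-day event falls on the cut date and can appear under HA.

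In addition, nothing says how crossover subjects enter a two-group rate that runs past crossover. These choices alter the counts behind a primary safety endpoint.

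**Working it through.** The plan states no figure on this point, so there is none to reproduce. The check sets the grouping boundaries against the treatment dates and then sizes the difference.

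1. **Pre-treatment window.** The schedule in Section 9 allows 60 days from consent to complete screening and 30 days from randomization to the index procedure: 60 + 30 = 90 days. Section 12.7.2 does not define enrollment. Section 8.4.3 dates the radiograph window from enrollment and a footnote to the schedule dates it from consent, which suggests that the two are the same. If enrollment meant randomization, the window would be 0 to 30 days and would exclude block events, because Section 10.1 confirms block response before randomizing.

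2. **Treatment to Visit 5.** Crossover follows the Visit 5 assessments, so crossover misattribution before that point is zero. Assigned and received treatment differ only for a subject given the other arm's treatment.

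3. **Visit 5 to Visit 5A.** The gap is 0 to 30 days. In Section 10.6, the 6-month "Visit/Visit 6 should occur at post-operative day 180 ± 14 days" after crossover. Share of later follow-up exposed = gap / (gap + follow-up after Visit 5A):
 - nominal: 30 / (30 + 180) = 30/210 = 14.3%
 - late Visit 6: 30 / (30 + 194) = 13.4%
 - early Visit 6: 30 / (30 + 166) = 15.3%
 - same-day crossover: 0%

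4. **Illustrative scale of the gap.** The HA arm is about 168/2 = 84. The crossover proportion is not given; assume 25% to 100%, that is 21 to 84 subjects, all at day 30. Exposed time is 21 × 30/365.25 = 1.7 to 84 × 30/365.25 = 6.9 person-years. Appendix 2 gives 26-week (182-day) rates for the HA product. Under a constant hazard, the 30-day probability is 1 − (1 − p)^(30/182).

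| Event | p over 26 weeks | 30-day probability | Subjects, 21 to 84 crossing over |
|---|---|---|---|
| Any treatment-emergent event | 70/123 = 56.9% | 13.0% | 2.7 to 10.9 |
| Injected-knee event | 44/123 = 35.8% | 7.0% | 1.5 to 5.9 |

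 These are upper bounds under those rates. The gap may be shorter or nil, and a gap event changes the Crossover proportion only if that subject has no event after the procedure.

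5. **Two-group overall rate.** On nominal visit days, a crossover subject has 180 days after HA, a gap of 0 to 30 days, and 180 days after CRFA. If that subject is counted under HA to final follow-up, the post-CRFA share of the time is 180/360 = 50% (no gap) down to 180/390 = 46% (30-day gap).

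6. **Direction.** Gap events add to Crossover. Same-day procedure events, and CRFA events in the two-group rate, add to HA. Nothing makes these cancel.

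**The case against.** The strongest reply is that the plan does not ignore crossover. After Visit 5 it gives Crossover its own stratum, distinct from randomized CRFA. Status can fairly be read as HA until the Visit 5A procedure and Crossover from then on. A same-day procedure must follow the Visit 5 items, so it belongs logically to the later period, and Section 10.6 treats same-day crossover as the exception. Sections 10.3 and 10.6 list adverse event assessments at Visits 5 and 5A respectively. Pre-treatment events are defined in Section 11.1.1, and block events precede assignment, so they should not systematically favour an arm. Onset dates are collected, and Section 12 promises a stand-alone SAP with detailed methods.

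Much of this stands. A reader might infer that all adverse events are analysed by randomized arm, that crossover events are necessarily charged to the wrong treatment, or that every crossover subject is affected. The documents do not support those readings. The arm rule covers only the first period, the switch date of Crossover status is undefined rather than wrong, and a same-day subject has no gap at all. Nor do the documents show that procedure-day events are the most likely CRFA events; Section 8.4.7 expects site discomfort for up to 1 to 2 weeks.

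The reply does not remove the point. Section 12.7.2 does state a rule that starts at enrollment and uses randomized assignment. The treatment-emergent definition is never applied in Section 12.7, and non-differential block events still raise both arms' rates. A date without a time cannot order same-day events, and Section 10.6 waives repeating overlapping assessments that day. No text says how crossover subjects enter the two-group rate. The stand-alone SAP may settle these matters, but its text is not in the documents reviewed.

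**Conclusion.** The point holds as a limited attribution weakness. Two parts follow from the text as written: pre-treatment events, over up to about 90 days if enrollment means consent, enter the arm tables; and first-period events of a wrongly treated subject are counted under the assigned arm. Three parts are possibilities left open by missing definitions: HA-only events listed under Crossover, same-day procedure events listed under HA, and a crossover subject's CRFA events counted under HA in the overall rate.

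The gap is at most about 14% of a crossover subject's later follow-up, 13% to 15% across the visit window. The subject counts are illustrative only, since they rest on an assumed crossover proportion, a full 30-day gap and a constant hazard borrowed from Appendix 2. The two-group rate through final follow-up is potentially the larger issue, because about half of a crossover subject's follow-up is after CRFA. Apart from possible same-day events, crossover does not disturb the comparison up to Visit 5.

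**What to change.** In Section 12.7.2, and in the stand-alone SAP:

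- Tabulate treatment-emergent events by the last study treatment received before onset: the initial treatment actually received until the Visit 5A procedure, and Crossover-CRFA from then on.
- List non-treatment-emergent events, including those from the diagnostic block, separately.
- Make the two-arm comparison of the overall rate on events before any crossover, and report Crossover as its own group.
- Where Visits 5 and 5A fall on the same day, record whether onset was before or after the procedure.

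This is a cheap improvement. Onset dates are already collected and no design change is needed. The cost is a few sentences, a little more programming and one eCRF field.
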